Level -2	25 Units/kg	5-fluorouracil 2400 mg/m² over 46 hours, oxaliplatin 85 mg/m², Irinotecan 150 mg/m²,leucovorin 400 mg/m2			
Level -1	50 Units/kg	5-fluorouracil 2400 mg/m² over 46 hours, oxaliplatin 85 mg/m², Irinotecan 150 mg/m²,leucovorin 400 mg/m2			
Level 0 (starting dose)	75 Units/kg	5-fluorouracil 2400 mg/m² over 46 hours, oxaliplatin 85 mg/m², Irinotecan 150 mg/m²,leucovorin 400 mg/m2			
Level 1	100 Units/kg	5-fluorouracil 2400 mg/m² over 46 hours, oxaliplatin 85 mg/m², Irinotecan 150 mg/m²,leucovorin 400 mg/m2			

Table 2

5.4 Definition of the Maximum Tolerated dose (MTD)

The maximum tolerated dose (MTD) is defined as the highest dose level where at most 1 of 6 patients experience a dose-limiting toxicity (DLT) during the first cycle. If 0 or 1 of 6 patients in Dose Level 1 experience DLT during the first cycles, Dose Level 1 will be presumed to be the MTD.

5.5 Dose Limiting Toxicities (DLT)

To the extent possible, any adverse events that are deemed to study drug-related and are ongoing at end of treatment will be followed up to resolution or until a determination is made that the unresolved event is stable.

In general, Grade 1 and 2 toxicities do not require any dose modification for any of the chemotherapy agents or for Eryaspase. However, appropriate supportive care will be provided for the management of drug-related toxicities.

Hematologic DLT is defined as any of the following that occurs during the first cycle (total of approximately 28 days) of treatment that is attributed as possibly, probably, or definitely related to Eryaspase alone or the combination of Eryaspase and FOLFIRINOX:

- Grade 4 neutrophil count decrease > 7 day duration
- Febrile neutropenia \geq Grade 3 of any duration
- Grade 3 or Grade 4 platelet count decrease
- Any Grade 4 platelet count decrease with bleeding

Non-hematologic DLT is defined as any grade 3 or grade 4 adverse event, based on NCI CTCAE that occurs during the first cycle (total of approximately 28 days) of treatment that is considered possibly, probably, or definitely related to Eryaspase alone or the combination of Eryaspase and FOLFIRINOX with the following specific exceptions:

- Grade 3 or 4 AST, ALT, alkaline phosphatase, or total bilirubin due to biliary obstruction or infection
- Grade 3 or 4 nausea, vomiting, or diarrhea resolved with maximal supportive care within 7 days
- Grade 3 mucositis resolved with supportive care
- Grade 3 fatigue lasting less than 7 days
- Grade 3 or 4 laboratory abnormalities that are not clinically significant or do not require any clinical intervention.

Any treatment-related toxicity that results in treatment delay for > 21 days cumulatively during the first cycle or > 14 days cumulatively during the second cycle will be considered a DLT, and the patient will be removed from the study. If the treatment delay during the first cycle is due to reasons other than treatment-related toxicity, the patient will be replaced as the subject will be considered to be inevaluable for DLT.

5.6 **Dose modification**

Dose reduction or modification are only allowed after passing the 28 days DLT period. Recommended mFOLFIRINOX dose modifications are listed in Table 3, however modification may follow investigator or institutional guidelines. Modifications may be made to any or all chemotherapy agents, per investigator discretion.

Table 3

Recommended mFOLFIRINOX Dose Modifications						
Drug	Initial dose	Dose Reduction	Dose			
		Level I	Level 2			
5-FU	2400 mg/m ²	1920 mg/m²	1600 mg/m²			
Irinotecan	150 mg/m²	125 mg/m ²	90 mg/m ²			
Oxaliplatin	85 mg/m ²	68 mg/m ²	50 mg/m ²			

Table 4. Indications for mFOLFIRINOX Dose Modifications

Table 4A

A Neutrophil Count Decreased		Hold treatment until recovery to at least Grade 1 for up to two weeks. If patient has not recovered to ≤ Grade 1 in two weeks, discontinue treatment. Follow drug specific modifications below for subsequent cycles	
Toxicity Grade	5-FU	Irinotecan	Oxaliplatin
2	Consider holding, but can treat per Investigator discretion.	Consider holding, but can treat per Investigator discretion.	Consider holding, but can treat per Investigator discretion.
3-4	1 st occurrence:	1 st occurrence:	1 st occurrence:
	reduce by 1 dose level	reduce by 1 dose level	reduce by 1 dose level
	2 nd occurrence:	2 nd occurrence:	2 nd occurrence:
	reduce by 1 dose level	reduce by 1 dose level	reduce by 1 dose level
	3 rd occurrence:	3 rd occurrence:	3 rd occurrence:
	discontinue the	discontinue the	discontinue the
	treatment	treatment	treatment

B Platelet Count Decreased		Hold treatment until recovery to ≤ Grade 1 for up to two weeks. If patient has not recovered to ≤ Grade 1 in two weeks, discontinue treatment. Follow drug specific modifications below for subsequent cycles	
Toxicity Grade	5-FU	Irinotecan	Oxaliplatin
2	Consider holding, but can treat per Investigator discretion.	Consider holding, but can treat per Investigator discretion.	Consider holding, but can treat per Investigator discretion.
3-4	1 st occurrence: reduce by 1 dose level 2 nd occurrence: reduce by 1 dose level 3 rd occurrence: discontinue the treatment	1 st occurrence: reduce by 1 dose level 2 nd occurrence: reduce by 1 dose level 3 rd occurrence: discontinue the treatment	1 st occurrence: reduce by 1 dose level 2 nd occurrence: reduce by 1 dose level 3 rd occurrence: discontinue the treatment

Table 4C

C General Non-hematologic toxicities		All treatment related non-hematological toxicities (with the exception of hair loss) should resolve to Grade 1 prior to starting next cycle of therapy
Toxicity Grade		
2	Consider holding, but can treat per Investigator discretion.	
3	Hold all drugs until resolution to ≤ Grade 1. Then resume treatment at the next lower dose level.	
4		Discontinue all protocol treatment

Table 4D

D Diarrhea		Patients should be instructed in the use of loperamide as treatment for diarrhea. Patient should not be retreated with irinotecan until recovery from diarrhea, without loperamide for at least 24 hours, has occurred
Toxicity Grade		
2	Consider holding, but can treat per Investigator discretion.	
	1st occurrenc	e: Reduce irinotecan by 1 dose level
3-4	2nd occurrent FU dose by 1	ce: Reduce oxaliplatin dose by 1 dose level and 5- dose level
	3rd occurrenc	e: Discontinue all protocol treatment

Table 4E

E Mucositis			
Toxicity Grade	5-F	FU	Oxaliplatin
2	Hold tre	eatment	Hold treatment
	until resolution	n to ≤ Grade 1,	until resolution to ≤ Grade 1,
	Continue at sa	ame dose level	Continue at same dose level
3-4	Hold tre	eatment	Hold treatment
	until resolution	n to ≤ Grade 1,	until resolution to ≤ Grade 1,
	Continue at ne	ext lower dose	Continue at next lowest dose
	lev	vel	level

Table 4F

F Oxaliplatin related neuropathy		Paresthesia or peripheral sensory neuropathy	
Toxicity Grade	Duration of toxicity 1–7 days	Duration of toxicity more than 7 day	Persistent (duration of toxicity more than 14 days)
2	No dose modification	No dose modification	Next lowest dose level for oxaliplatin
3	Next lowest dose level for oxaliplatin	Next lowest dose level for oxaliplatin	Discontinue
4	Discontinue	Discontinue	Discontinue

Table 4G

G		
Palmar-plantar erythrodysesthesia syndrome		
Toxicity Grade 2	Consider holding	, but can treat per Investigator discretion.
Toxicity Grade 3-4	Rec	luce 5–5-FU by 1 dose level

5.7 Discontinuation of Eryaspase

- DLT during dose escalation
- Study completion
- Patient withdraws from the study for any reason, including withdraws consent.
- Progressive disease
- Declared discontinuation due to missed Eryaspase doses.

5.8 Duration of therapy

If at any time the constraints of this protocol are considered to be detrimental to the patient's health and/or the patient no longer wishes to continue protocol therapy, the protocol therapy should be discontinued and the reason(s) for discontinuation documented in the case report forms.

Version 2.1, 16 March 2022

In the absence of treatment delays due to adverse events, treatment may continue for a total of 12 treatments of FOLFIRINOX (approximately 6 months) or until one of the following criteria applies:

- Documented and confirmed disease progression
- Death
- Adverse event(s) that, in the judgment of the investigator, may cause severe or permanent harm or which rule out the continuation of study drug
- General or specific changes in the patient's condition render the patient unacceptable for further treatment in the judgment of the investigator
- Suspected pregnancy
- Serious non-compliance with the study protocol
- Lost to follow-up
- Patient withdraws consent
- Investigator removes the patient from the study
- The Sponsor-Investigator or Georgetown decides to close the study

After 12 treatments of FOLFIRINOX, patients have the option to continue FOLFIRINOX plus Eryaspase or can transition to FOLFIRI (dropping Oxaliplatin) plus Eryaspase or 5-FU (dropping Irinotecan and Oxaliplatin) plus Eryaspase, at the investigator's discretion.

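### The Grade 3 mucositis exception to the DLT definition has no time limit, so an episode of several weeks may escape the DLT count, and the status of an episode open at the 4-week decision is not stated

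*Combined protocol and SAP*

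**What the plan says.** Section 5.5 of the combined protocol and SAP counts as a non-hematologic DLT any Grade 3 or 4 event that is at least possibly related to Eryaspase or the combination and that "occurs during the first cycle (total of approximately 28 days) of treatment". Five exceptions follow. Three depend on how the event runs:

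- The mucositis exception, which is the one at issue, reads "Grade 3 mucositis resolved with supportive care".
- The entry just above it in the list sets a limit in days: "Grade 3 or 4 nausea, vomiting, or diarrhea resolved with maximal supportive care within 7 days".
- The entry just below it does so too: "Grade 3 fatigue lasting less than 7 days".

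The other two depend on cause or clinical relevance. The first of these covers "Grade 3 or 4 AST, ALT, alkaline phosphatase, or total bilirubin due to biliary obstruction or infection", and the second, which closes the list, covers "Grade 3 or 4 laboratory abnormalities that are not clinically significant or do not require any clinical intervention".

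The next paragraph adds a delay rule from which mucositis is not exempt. It covers "Any treatment-related toxicity that results in treatment delay for > 21 days cumulatively during the first cycle", and for the following cycle a delay of "> 14 days cumulatively during the second cycle will be considered a DLT".

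Section 5.3 permits escalation once all patients at the current dose have been observed for at least 4 weeks. Under Sections 5.3 and 5.4, a level with at most 1 DLT in 6 patients can be the MTD, and 2 DLTs place a level above it.

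**The concern.** Determining the MTD is part of the primary objective, and it rests on a count of DLTs in cohorts of 3 or 6. Whether an event counts should therefore be clear from the text and settled when the decision is made. The mucositis exception falls short in two ways.

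First, it asks only that the event resolved, without saying by when, so a prolonged related toxicity can drop out of the count. Diarrhea of the same grade that outlasts 7 days stays in. No section explains the difference.

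Second, an episode still open when the 4-week observation ends has not yet met the condition for exemption but may meet it later. The protocol does not say how such a patient is classified at the decision. Two sites could classify the same patient differently. Section 5.7 also lists a DLT during escalation as a reason to discontinue Eryaspase, so the ambiguity reaches the individual patient as well as the cohort.

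**Working it through.** There is no planned figure to reproduce: the documents give no mucositis rate, DLT rate or operating characteristic for the 3+3 rule. The check is a comparison of the text, day arithmetic and a labelled illustration.

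**1. The five exceptions side by side (Section 5.5)**

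| Exception | Grades exempt | Depends on | Time limit |
|---|---|---|---|
| Liver tests | 3–4 | cause | none |
| Nausea, vomiting, diarrhea | 3–4 | resolution | 7 days |
| Mucositis | 3 only | resolution | none |
| Fatigue | 3 only | duration | under 7 days |
| Laboratory abnormalities | 3–4 | clinical relevance | none |

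Two other exceptions also lack a limit, but neither turns on resolution or duration. Mucositis is the only one that does so without a limit.

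**2. What the delay rule catches**

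Inputs: doses on Day 1 and Day 15 of a 4-week cycle (Section 5.3), so Cycle 2 Day 1 falls on Day 29; delay limits of 21 and 14 days (Section 5.5). Table 4E recommends holding 5-FU and oxaliplatin until Grade 1 or lower and states no maximum hold. I assume treatment is held for the mucositis and ignore the ±1-day dosing window.

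- A 20-day episode from Day 2 ends at about Day 2 + 20 = Day 22. The Day 15 dose is about 22 − 15 = 7 days late, so the rule is not met and there is no DLT.
- In general, a held Day 15 dose passes the limit only after Day 15 + 21 = Day 36. The longest episode not caught is 36 − 2 = 34 days for onset on Day 2, and 36 − 8 = 28 days for onset on Day 8.
- With onset after the Day 15 dose, the next dose is due on Day 29. The rule acts after Day 29 + 14 = Day 43 or Day 29 + 21 = Day 50, depending on the cycle to which the delay is charged. For onset on Day 22, the longest episode not caught is 21 or 28 days.

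Each trigger falls after the earliest 4-week decision point. If treatment is not held, the rule does not act at all, because it measures delay of treatment and not duration of toxicity.

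**3. When each exception is settled**

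A 7-day exception with onset as late as Day 28 is settled by about Day 28 + 7 = Day 35. The mucositis exception has no such end date.

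**4. Effect on a decision**

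One event changes 0/3 (escalate) to 1/3 (enroll 3 more at the level), or 1/6 (acceptable) to 2/6 (above the MTD).

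**5. Illustration (rates are assumptions)**

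A level passes with 0/3, or with 1/3 followed by 0/3. If p is the DLT probability per patient:

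P(pass) = (1−p)³ + 3p(1−p)² × (1−p)³ = (1−p)³ + 3p(1−p)⁵

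Start from p = 0.20 without the exempted events, and add the share of patients whose only candidate DLT is exempted prolonged mucositis:

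| Added points | p | (1−p)³ | 3p(1−p)⁵ | P(pass) |
|---|---|---|---|---|
| 0 | 0.20 | 0.512 | 0.197 | 0.709 |
| 1 | 0.21 | 0.493 | 0.194 | 0.687 |
| 2 | 0.22 | 0.475 | 0.191 | 0.665 |
| 5 | 0.25 | 0.422 | 0.178 | 0.600 |
| 10 | 0.30 | 0.343 | 0.151 | 0.494 |

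For starting rates from 10% to 25%, adding 3, 5 or 10 points lowers the pass probability by about 5–7, 9–11 or 20–21 points.

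**The case against.** **The delay rule is a backstop.** A reader might infer that prolonged Grade 3 mucositis can never be a DLT once it resolves. The text does not support that. A delay beyond the stated limits makes the event a DLT whatever its later course, and related Grade 4 mucositis is a DLT throughout. This stands and bounds the point. The backstop is loose and late, however, and the 20-day example passes beneath it.

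**Later revision would not be unsafe.** A reader might also infer that the count can be revised after escalation, to the patients' detriment. Read literally, an episode open at Day 28 has not resolved and so counts as a DLT at the decision. Later resolution could only lower the count, and no section provides for withdrawing a DLT already counted. This stands too. What remains is that the status at the decision is left to inference.

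**Late settlement is not peculiar to mucositis.** Diarrhea or fatigue starting late in cycle 1 can also run past Day 28, and the cycle 2 delay rule is necessarily settled later. This is correct. Only the lack of any end date is specific to mucositis.

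**Different limits may be deliberate.** The mucositis exception stops at Grade 3, whereas the nausea/vomiting/diarrhea exception extends to Grade 4. A choice of this kind is possible, but the protocol does not state one, and it would not resolve the question of open events.

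**The size is conjecture.** The relevant group is narrow: Grade 3, prolonged, in cycle 1, related, resolved, not caught by the delay rule, and in a patient with no other DLT. The common adverse events listed in Section 9.1.1 do not include mucositis. This stands, and it is why the illustration starts at 1 point.

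**Conclusion.** The point holds as a gap in a rule that feeds the primary 3+3 count. Followed as written, a related Grade 3 mucositis episode of several weeks is not a DLT unless treatment is delayed beyond the stated limits, while Grade 3 diarrhea unresolved after 7 days is. The durations in the working assume that treatment is held as Table 4E recommends.

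For a single cohort the size is certain: one event can change the decision. Across repeated use it is not known. At an assumed 20% rate of other DLTs, the chance of passing a level falls from 71% to 69–67% if 1–2 points are added, and to 60–49% if 5–10 points are added. These figures assume that the mucositis events fall in patients with no other DLT; no rate in the documents favors either end of the range.

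The documents do not support reading the exception as a complete exemption for resolved mucositis, or as a route to unsafe escalation through a count revised afterwards. The amendment is worth making because the rule decides the primary result and is cheap to clarify.

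**What to change.** Reconcile the mucositis exception in Section 5.5 with the adjacent time-limited exceptions, the delay rule and the 4-week decision point in Section 5.3:

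1. Give the mucositis exception a time limit, in the same form as its neighbors. The number is for the sponsor to set; none is proposed here.
2. State that any event whose exception is still open at the end of cycle 1 is classified before the escalation decision, and that this classification is final. This also covers late-onset diarrhea and fatigue.

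The cost is a one-line amendment and at most a short wait when an event is open at Day 28. Section 5.3 already sets 4 weeks as a minimum, so such a wait fits the present design.

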5.9 Duration of follow-up

Patients will be followed via chart review or phone interview every 8 weeks for a total of 2 years or until death, whichever occurs first. Patients removed from study for unacceptable adverse events will be followed until resolution or stabilization of the adverse event.

5.10 Women of childbearing potential

Women of childbearing potential (women with regular menses, women with amenorrhea, women with irregular cycles, women using a contraceptive method that precludes withdrawal, or women who have had a tubal ligation) are required to have a negative serum pregnancy test within 14 days prior to the first dose of Eryaspase.

Female and male patients (along with their female partners) are required to use two forms of acceptable contraception, including one barrier method, during participation in the study and for 1 month following the last dose of Eryaspase.

If a patient is suspected to be pregnant, Eryaspase should be immediately discontinued. In addition, a positive urine test must be confirmed by a serum pregnancy test. If it is confirmed that the patient is not pregnant, the patient may resume dosing.

If a female patient or female partner of a male patient becomes pregnant during therapy or within 1 month after the last dose of Eryaspase, the investigator must be notified in order to facilitate outcome follow-up.

5.11 Study Pause Criteria

The protocol will be paused with any criteria below being met:

- Any death (other than due to progressive disease)
- The occurrence of 2 or more grade 4 events

6. Study Population

6.1 Inclusion Criteria

Patients must meet all of the following inclusion criteria to participate in this study:

- 6.1.1 Patient must be able to understand and willing to sign an IRB approved written informed consent document.
- 6.1.2 Patient must have histologically or cytologically confirmed pancreatic adenocarcinoma, which is locally advanced, unresectable, or metastatic.
- 6.1.3 Patient must have received no previous surgery, chemotherapy, radiotherapy or investigational therapy for the treatment of locally advanced or metastatic disease.
- 6.1.4 If a patient has had adjuvant/neoadjuvant therapy for localized disease, tumor recurrence or disease progression must have occurred no sooner than 6 months after completing the last dose of the aforementioned therapies.
- 6.1.5 Patient must have radiographically measurable disease according to RECIST 1.1
- 6.1.6 Patient must be > 18 years of age.
- 6.1.7 Patient must have a life expectancy of \geq 3 months.
- 6.1.8 Patient must have an ECOG performance status \leq 1.
- 6.1.9 Patient must have normal bone marrow and organ function as defined below:

0	Absolute neutrophil count	> 1,500/mcl
0	Platelets	> 100,000/mcl
0	Hemoglobin	> 9.0 g/dL
0	Serum Albumin	>3.0 g/dL

- Creatinine should be below the upper limit of normal OR Creatinine clearance (eGFR) >60 mL/min/1.73 m2 for patients with creatinine levels above institutional normal
- Plasma antithrombin III > 65%, fibrinogen > 150 mg/dL (1.5g/L), international normalized ratio (INR) < 1.5, and partial thromboplastin time (PTT) < institutional ULN.
- Total bilirubin \leq 2.0x institutional ULN
- 6.1.10 Patients who have had a stent placed for biliary obstruction can be included in the study.
- 6.1.11 Female subject of childbearing potential must have a negative urine or serum pregnancy test.

- 6.1.12 Women of childbearing potential and men must agree to use adequate contraception (hormonal or barrier method of birth control, abstinence) prior to study entry and for the duration of study participation. Should a woman become pregnant or suspect she is pregnant while participating in this study, she must inform her treating physician immediately.
- 6.1.13 Male subjects with a female partner of childbearing potential must agree to use two adequate methods or a barrier method plus a method of contraception

6.2 Exclusion Criteria

Patients meeting any of the following exclusion criteria will not be able to participate in this study:

- 6.2.1 Evidence of neuroendocrine tumor, duodenal adenocarcinoma, or ampullary adenocarcinoma.
- 6.2.2 History of other malignancy \leq 3 years ago, with the exception of basal cell or squamous cell carcinoma of the skin, which were treated with local resection only or carcinoma in situ of the cervix of ductal carcinoma in situ.
- 6.2.3 Receiving any other investigational agents 28 days prior to the screening process.
- 6.2.4 Patient with evidence of brain metastases. Such patients must be excluded from this clinical trial because of their poor prognosis and because they often develop progressive neurologic dysfunction that would confound the evaluation of neurologic and other adverse events.
- 6.2.5 History of allergic reactions attributed to compounds of similar chemical or biologic composition to asparaginase, 5FU, oxaliplatin, or irinotecan.
- 6.2.6 Any uncontrolled intercurrent illness including, but not limited to, ongoing or active infection, symptomatic congestive heart failure, unstable angina pectoris, cardiac arrhythmia, any clinically active malabsorption syndrome, inflammatory bowel disease, any condition that increases the risk of severe irinotecan gastrointestinal toxicity, or psychiatric illness/social situations that would limit compliance with study requirements
- 6.2.7 Has an active autoimmune disease, or a documented history of autoimmune disease or syndrome that requires steroids or immunosuppressive agents. Subjects with vitiligo or resolved childhood asthma/atopy would be an exception to this rule.
- 6.2.8 History of abdominal fistula, gastrointestinal perforation, peptic ulcer, or intraabdominal abscess within 6 months prior to randomization.
- 6.2.9 Has had an allogeneic tissue/solid organ transplant.
- 6.2.10 Has received or will receive a live vaccine within 30 days prior to the first administration of study medication. Seasonal flu vaccines that do not contain live virus are permitted
- 6.2.11 Has known active Hepatitis B or C.
- 6.2.12 Patient is pregnant and/or breastfeeding.
- 6.2.13 Known to be HIV-positive on combination antiretroviral.

6.3 Randomization and Method of Treatment Assignment

There is only one treatment group in each part of the study. Therefore, no randomization will be performed

